10.3.4. Reporting of SAEs

[figure not shown]
SAE Reporting to Pfizer Safety via an Electronic Data Collection Tool

[figure not shown]
- The primary mechanism for reporting an SAE to Pfizer Safety will be the electronic data collection tool.
- If the electronic system is unavailable, then the site will use the paper SAE data collection tool (see next section) to report the event within 24 hours.
- The site will enter the SAE data into the electronic system as soon as the data become available.
- After the study is completed at a given site, the electronic data collection tool will be taken off-line to prevent the entry of new data or changes to existing data.
- If a site receives a report of a new SAE from a study participant or receives updated data on a previously reported SAE after the electronic data collection tool has been taken off-line, then the site can report this information on a paper SAE form (see next section) or to Pfizer Safety by telephone.

SAE Reporting to Pfizer Safety via Vaccine SAE Reporting Form

- Facsimile transmission of the Vaccine SAE Reporting Form is the preferred method to transmit this information to Pfizer Safety.
- In circumstances when the facsimile is not working, notification by telephone is acceptable with a copy of the Vaccine SAE Reporting Form sent by overnight mail or courier service.
- Initial notification via telephone does not replace the need for the investigator to complete and sign the Vaccine SAE Reporting Form pages within the designated reporting time frames.

10.5. Appendix 5: Liver Safety: Suggested Actions and Follow-Up Assessments Potential Cases of Drug-Induced Liver Injury

Humans exposed to a drug who show no sign of liver injury (as determined by elevations in transaminases) are termed "tolerators," while those who show transient liver injury but adapt are termed "adaptors." In some participants, transaminase elevations are a harbinger of a more serious potential outcome. These participants fail to adapt and therefore are "susceptible" to progressive and serious liver injury, commonly referred to as DILI. Participants who experience a transaminase elevation above 3 × ULN should be monitored more frequently to determine if they are "adaptors" or are "susceptible."

LFTs are not required as a routine safety monitoring procedure in this study. However, should an investigator deem it necessary to assess LFTs because a participant presents with clinical signs/symptoms, such LFT results should be managed and followed as described below.

In the majority of DILI cases, elevations in AST and/or ALT precede TBili elevations (>2 × ULN) by several days or weeks. The increase in TBili typically occurs while AST/ALT is/are still elevated above 3 × ULN (ie, AST/ALT and TBili values will be elevated within the same laboratory sample). In rare instances, by the time TBili elevations are detected, AST/ALT values might have decreased. This occurrence is still regarded as a potential DILI. Therefore, abnormal elevations in either AST OR ALT in addition to TBili that meet the criteria outlined below are considered potential DILI (assessed per Hy's law criteria) cases and should always be considered important medical events, even before all other possible causes of liver injury have been excluded.

The threshold of laboratory abnormalities for a potential DILI case depends on the participant's individual baseline values and underlying conditions. Participants who present with the following laboratory abnormalities should be evaluated further as potential DILI (Hy's law) cases to definitively determine the etiology of the abnormal laboratory values:

- Participants with AST/ALT and TBili baseline values within the normal range who subsequently present with AST OR ALT values >3 × ULN AND a TBili value >2 × ULN with no evidence of hemolysis and an alkaline phosphatase value <2 × ULN or not available.
- For participants with baseline AST **OR** ALT **OR** TBili values above the ULN, the following threshold values are used in the definition mentioned above, as needed, depending on which values are above the ULN at baseline:
 - Preexisting AST or ALT baseline values above the normal range: AST or ALT values >2 times the baseline values AND >3 × ULN; or >8 × ULN (whichever is smaller).

• Preexisting values of TBili above the normal range: TBili level increased from baseline value by an amount of at least 1 × ULN **or** if the value reaches >3 × ULN (whichever is smaller).

Rises in AST/ALT and TBili separated by more than a few weeks should be assessed individually based on clinical judgment; any case where uncertainty remains as to whether it represents a potential Hy's law case should be reviewed with the sponsor.

The participant should return to the investigator site and be evaluated as soon as possible, preferably within 48 hours from awareness of the abnormal results. This evaluation should include laboratory tests, detailed history, and physical assessment.

In addition to repeating measurements of AST and ALT and TBili for suspected Hy's law cases, additional laboratory tests should include albumin, CK, direct and indirect bilirubin, GGT, PT/INR, total bile acids, and alkaline phosphatase. Consideration should also be given to drawing a separate tube of clotted blood and an anticoagulated tube of blood for further testing, as needed, for further contemporaneous analyses at the time of the recognized initial abnormalities to determine etiology. A detailed history, including relevant information, such as review of ethanol, acetaminophen/paracetamol (either by itself or as a coformulated product in prescription or over-the-counter medications), recreational drug, or supplement (herbal) use and consumption, family history, sexual history, travel history, history of contact with a jaundiced person, surgery, blood transfusion, history of liver or allergic disease, and potential occupational exposure to chemicals, should be collected. Further testing for acute hepatitis A, B, C, D, and E infection, liver imaging (eg, biliary tract), and collection of serum samples for acetaminophen/paracetamol drug and/or protein adduct levels may be warranted.

All cases demonstrated on repeat testing as meeting the laboratory criteria of AST/ALT and TBili elevation defined above should be considered potential DILI (Hy's law) cases if no other reason for the LFT abnormalities has yet been found. Such potential DILI (Hy's law) cases are to be reported as SAEs, irrespective of availability of all the results of the investigations performed to determine etiology of the LFT abnormalities.

A potential DILI (Hy's law) case becomes a confirmed case only after all results of reasonable investigations have been received and have excluded an alternative etiology.

10.6. Appendix 6: AEs, ADEs, SAEs, SADEs, USADEs, and Device Deficiencies: Definitions and Procedures for Recording, Evaluating, Follow-Up, and Reporting in Medical Device Studies

Definitions of a Medical Device Deficiency

The definitions and procedures detailed in this appendix are in accordance with ISO 14155 and the European MDR 2017/745 for clinical device research (if applicable).

Both the investigator and the sponsor will comply with all local reporting requirements for medical devices.

The detection and documentation procedures described in this protocol apply to all sponsor medical devices provided for use in the study (see Section 6.1.2 for the list of sponsor medical devices).

10.6.1. Definition of AE and ADE

AE and ADE Definition

- An AE is defined in Appendix 3 (Section 10.3.1).
- An ADE is defined as an AE related to the use of an investigational medical device. This definition includes any AEs resulting from insufficient or inadequate instructions for use, deployment, implantation, installation, or operation, or any malfunction of the investigational medical device as well as any event resulting from use error or from intentional misuse of the investigational medical device.

10.6.2. Definition of SAE, SADE, and USADE

SAE Definition

• An SAE is defined in Appendix 3 (Section 10.3.2).

SADE Definition

- An SADE is defined as an adverse device effect that has resulted in any of the consequences characteristic of an SAE.
- Any device deficiency that might have led to an SAE if appropriate action had not been taken, intervention had not occurred, or circumstances had been less fortunate.

USADE Definition

A USADE is a serious adverse device effect that by its nature, incidence, severity,
or outcome has not been identified in the current version of the risk analysis
management file.

10.6.3. Definition of Device Deficiency

Device Deficiency Definition

 A device deficiency is an inadequacy of a medical device with respect to its identity, quality, durability, reliability, safety, or performance. Device deficiencies include malfunctions, use errors, and inadequate information supplied by the manufacturer.

10.6.4. Recording/Reporting and Follow-Up of Medical Device Deficiencies

Device Deficiency Recording

- When a device deficiency occurs, it is the responsibility of the unblinded site staff to review all documentation (eg, hospital progress notes, laboratory reports, and diagnostic reports) related to the event.
- The unblinded site staff will then record all relevant device deficiency information in the participant's medical records, in accordance with the investigator's normal clinical practice and will also capture the required information on the Medical Device Complaint form.
- It is **not** acceptable for the investigator to send photocopies of the participant's medical records to Pfizer Safety in lieu of following the reporting process described in the Medical Device Complaint form.
- There may be instances when copies of medical records for certain cases are requested by Pfizer Safety. In this case, all participant identifiers, with the exception of the participant number, will be redacted on the copies of the medical records before submission to Pfizer Safety.
- If the unblinded site staff determines that the medical device deficiency may have injured the participant (ie, the medical device deficiency is associated with an AE or SAE), then the unblinded site staff will attempt to establish a diagnosis of the event based on signs, symptoms, and/or other clinical information. Whenever possible, the diagnosis will be documented in the participant's medical record and recorded as the AE or SAE rather than the individual signs/symptoms.

Requirements for recording and reporting an AE or SAE are provided in Appendix 3 (Section 10.3.3).

- For device deficiencies, it is very important that the unblinded site staff describes any corrective or remedial actions taken to prevent recurrence of the incident.
 - A remedial action is any action other than routine maintenance or servicing of a medical device where such action is necessary to prevent recurrence of a device deficiency. This includes any amendment to the device design to prevent recurrence.

Assessment of Causality Occurring in Conjunction With a Medical Device Deficiency

- If an AE or SAE has occurred in conjunction with a medical device deficiency, the investigator must assess the relationship between each occurrence of the AE or SAE and the medical device deficiency. The investigator will use clinical judgment to determine the relationship.
- A "reasonable possibility" of a relationship conveys that there are facts, evidence, and/or arguments to suggest a causal relationship, rather than a relationship cannot be ruled out.
- Alternative causes, such as underlying disease(s), concomitant therapy, and other risk factors, as well as the temporal relationship of the event to study intervention administration will be considered and investigated.
- The investigator will also consult the IB in his/her assessment.
- For each device deficiency, the investigator must document in the medical notes that he/she has reviewed the device deficiency and has provided an assessment of causality.
- There may be situations in which an SAE has occurred and the investigator has minimal information to include in the initial report to the sponsor. However, it is very important that the investigator always make an assessment of causality for every event before the initial transmission of the SAE data to the sponsor.
- The investigator may change his/her opinion of causality in light of follow-up information and send an SAE follow-up report with the updated causality assessment.
- The causality assessment is one of the criteria used when determining regulatory reporting requirements.

Follow-Up of Medical Device Deficiency

- The investigator is obligated to perform or arrange for the conduct of supplemental measurements and/or evaluations, as medically indicated or as requested by the sponsor to elucidate the nature and/or causality of the device deficiency as fully as possible. This may include additional laboratory tests or investigations, histopathological examinations, or consultation with other healthcare providers.
- New or updated information regarding the nature of the device deficiency will be recorded in the originally completed Medical Device Complaint form.
- New or updated information regarding any SAE that was potentially associated with the medical device deficiency will be submitted to Pfizer Safety on the Vaccine SAE Reporting Form within 24 hours of receipt of the information, according to the requirements provided in Appendix 3.

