6.1. Study Intervention(s) Administered

Study Interventions(s)						
Intervention Name	20vPnC	BNT162b2 (BNT162 RNA-LNP vaccine utilizing modRNA and encoding the P2 S)	Saline control			
Type	Vaccine	Vaccine	Placebo			
Dose Formulation	Sterile liquid suspension formulation containing saccharides from pneumococcal serotypes 1, 3, 4, 5, 6A, 6B, 7F, 8, 9V, 10A, 11A, 12F, 14, 15B, 18C, 19A, 19F, 22F, 23F, and 33F individually conjugated to CRM ₁₉₇	modRNA; frozen-liquid	Sterile normal saline solution for injection (0.9% sodium chloride injection)			

Study Interventions(s)					
CCI					
Route of Administration	Intramuscular injection	Intramuscular injection	Intramuscular injection		
Sourcing	Provided centrally by the sponsor	Provided centrally by the sponsor	Provided centrally by the sponsor		
Packaging and Labeling	Study intervention will be provided in single-use PFSs. Each PFS will be labeled as required per local and legal requirement. Cartons will include a blinded label and a tamper-evident seal.	Study intervention will be provided in glass vials. Each vial will be labeled as required per local and legal requirement. Cartons will include a blinded label and a tamper-evident seal.	Study intervention will be provided in single-use PFSs or glass vials. Each PFS or vial will be labeled as required per local and legal requirement. Cartons will include a blinded label and a tamper-evident seal.		

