6.1.1. Administration

Participants will receive study intervention at Visit 1 in accordance with the study's SoA.

At Visit 1, participants will receive a single 0.5-mL dose of either 20vPnC or saline injected intramuscularly into the right deltoid, and a single 0.3-mL dose of either BNT162b2 or saline injected intramuscularly into the left deltoid.

All vaccines will be prepared and administered by third-party unblinded site staff member(s) and will be administered to blinded participants. All other study personnel including the PI will be blinded. The unblinded site staff members will not participate in participant assessments.

Standard vaccination practices must be observed and vaccine must not be injected into blood vessels. Appropriate medication and other supportive measures for management of an acute hypersensitivity reaction should be available in accordance with local guidelines for standard immunization practices.

Administration of study interventions should be performed by an appropriately qualified, GCP-trained, and vaccine-experienced member of the study staff (eg, physician, nurse, physician's assistant, nurse practitioner, pharmacist, or medical assistant) as allowed by local, state, and institutional guidance.

Study intervention administration details will be recorded on the CRF.

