6.1.2. Medical Devices

In this study, medical devices being deployed are the PFSs containing 20vPnC or saline. Instructions for medical device use are provided in the IP manual.

[figure not shown]
All medical device deficiencies (including malfunction, use error, and inadequate labeling) shall be documented and reported by the unblinded site staff throughout the clinical investigation (see Section 8.3.9) and appropriately managed by the sponsor.

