6.3. Measures to Minimize Bias: Randomization and Blinding

As the appearances, storage conditions, preparation methods, and dose volumes of 20vPnC, BNT162b2, and saline are different, the study interventions will be prepared and administered by a designated third-party—unblinded site staff member. All other study personnel, including the PI, and the participant will be blinded. The unblinded site staff member(s) will not participate in participant assessments. See Section 6.3.2 and Section 6.3.3 for more details on blinding of site personnel members and sponsor.

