6.3.2. Blinding of Site Personnel

The study staff receiving, storing, dispensing, preparing, and administering the study interventions will be unblinded. All other study and site personnel, including the investigator, investigator staff, and participants, will be blinded to study intervention assignments. In particular, the individuals who evaluate participant safety will be blinded. Additionally, because there are differences in physical appearance, preparation timing, and dose volumes of 20vPnC, BNT162b2, and saline placebo, the study intervention will be prepared and administered in a manner that prevents the study participants from identifying the vaccine group based on the study intervention's appearance. This includes approximate alignment of dose preparation timing for 20vPnC and saline placebo with that of BNT162b2, which requires 30 minutes to thaw. Refer to the IP Manual for additional instructions.

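### Protocol 10.6.4 has unblinded site staff judge injury and diagnose AEs linked to a prefilled-syringe deficiency, against the blinding rules in 6.1.1, 6.3 and 6.3.2

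*Protocol*

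**What the plan says.** The blinding rule appears three times in the protocol. Section 6.1.1: "The unblinded site staff members will not participate in participant assessments". Section 6.3: "The unblinded site staff member(s) will not participate in participant assessments". Section 6.3.2, after defining the unblinded group ("The study staff receiving, storing, dispensing, preparing, and administering the study interventions will be unblinded"), adds: "In particular, the individuals who evaluate participant safety will be blinded".

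Section 10.6.4 (Appendix 6) covers device deficiencies. It has the unblinded site staff review the clinical documentation and write the deficiency information into the participant's medical records as well as on the Medical Device Complaint form. It then continues: "If the unblinded site staff determines that the medical device deficiency may have injured the participant", as shown by an associated AE or SAE, "then the unblinded site staff will attempt to establish a diagnosis of the event based on signs, symptoms, and/or other clinical information". Where possible, that diagnosis goes into the medical record and is recorded as the AE or SAE. The section refers to 10.3.3 for recording and reporting requirements. It leaves the causal link between event and deficiency to the investigator, who must also note in the medical record that each deficiency was reviewed.

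Section 10.3.3 (Appendix 3) assigns the diagnosis of any AE or SAE to the investigator, in nearly the same terms as 10.6.4 uses for the unblinded staff. Section 8.3.9 states that AEs and SAEs associated with a deficiency are handled like any others.

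On supply, 6.1.2 says: "In this study, medical devices being deployed are the PFSs containing 20vPnC or saline". The BNT162b2 entry in the 6.1 table says: "Study intervention will be provided in glass vials". Saline may come in either container. Section 6.1.1 fixes the arms: 20vPnC or saline on the right, BNT162b2 or saline on the left.

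**The concern.** Deciding whether a participant was injured, and naming the event from signs and symptoms, is a safety assessment. AEs and SAEs are primary endpoints (protocol Section 3), and SAP 6.1.1.3 and 6.1.1.4 tabulate them by system organ class and preferred term. The diagnosis entered therefore determines the row in which an event is counted. Under 10.6.4 that step can be taken by someone who knows the assignment, in a study described as double-blind.

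There is a second, smaller issue. Deficiency details go into a medical record open to the blinded investigator, who is in turn required to review each deficiency. Because container type depends on the product, those details can sometimes point to the vaccine group.

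**Working it through.** The plan gives no figure on this point, so the check is a comparison of sections.

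**Step 1: who does what.**

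| Task for a device-associated AE | 6.1.1, 6.3, 6.3.2 | 8.3.9 with 10.3.3 | 10.6.4 |
|---|---|---|---|
| Decide whether the participant may have been injured | Blinded staff | Usual AE process, under the investigator | Unblinded staff |
| Establish the diagnosis | Blinded staff | Investigator | Unblinded staff |
| Assess intensity | Blinded staff | Investigator | Not reassigned |
| Assess causality to the deficiency | Not addressed | Not addressed specifically | Investigator |
| Describe the deficiency itself | Not addressed | Unblinded staff (8.3.9) | Unblinded staff |

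The first two rows conflict. The investigator is blinded under 6.3.2, so the first two columns of rules agree with each other and 10.6.4 is the outlier. None of these sections states an exception for device events. The remaining rows raise no conflict.

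**Step 2: can the recorded details reveal the group?** Containers by group, from 6.1 and 6.1.1:

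- Coadministration: right arm 20vPnC (syringe), left arm BNT162b2 (vial).
- 20vPnC-only: right arm 20vPnC (syringe), left arm saline.
- BNT162b2-only: right arm saline, left arm BNT162b2 (vial).

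Section 6.1 does not say which saline container is used where, so both cases are needed:

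| Saline used | Left-arm syringe deficiency | Right-arm syringe deficiency |
|---|---|---|
| Prefilled syringe | Only 20vPnC-only is possible | All three groups are possible |
| Vial | Cannot occur | Coadministration or 20vPnC-only |

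So the group is identified in one cell only: a left-arm deficiency with syringe-supplied saline. With vial-supplied saline, a right-arm deficiency rules out one group and leaves two. Each inference also requires that the arm be known, and 10.6.4 does not say whether the record must include it.

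**Step 3: reach into the endpoints.** The diagnosis step applies only where a deficiency may have caused injury, which is a subset of all deficiencies. Prompted local reactions and systemic events are entered by participants in the e-diary (8.2.1) and are not affected. For AEs and SAEs the estimand is the percentage of participants reporting them. A change in how an event is diagnosed mainly moves it between preferred terms or organ classes and seldom alters whether the participant counts as having any AE.

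**The case against.** The best defence is that the protocol already routes these events correctly. Section 8.3.9 sends device-associated AEs through the ordinary process, 10.6.4 itself refers to 10.3.3, and the investigator keeps intensity and causality. The study is descriptive with no hypothesis tests, few events can be involved, and the IP manual or the complaint form, neither of which is available here, may limit what is disclosed. It is also sensible that unblinded staff describe the syringe fault, since they handle the syringes.

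Most of this stands as a limit on size. It does not remove the conflict: the cross-reference to 10.3.3 follows an instruction that assigns the diagnosis to someone else, and a site reading 10.6.4 is told to act against 6.1.1 and 6.3.

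A reader might infer more than the documents support, in four ways:

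- That these diagnoses will be made unblinded. The documents assign the task twice, so which instruction a site would follow is unsettled.
- That the investigator can generally read the group from the record. Step 2 shows that this holds in one configuration, if the arm is recorded.
- That a stated share of participants is affected. The documents give no deficiency rate, and a count of all deficiencies would exceed the number with an associated AE.
- That the vaccinators in particular make the diagnosis. The text refers to unblinded site staff, who under 6.3.2 also include those receiving, storing, dispensing and preparing the interventions.

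**Conclusion.** The contradiction is real. Section 10.6.4 gives unblinded staff the injury determination and the diagnosis of device-associated AEs. Sections 6.1.1, 6.3 and 6.3.2 exclude them from such work, and 8.3.9 with 10.3.3 place it with the blinded investigator. All of these cannot be followed together.

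Its size is small. It covers only AEs associated with a prefilled-syringe deficiency. That these are probably few is a judgement, since the plan offers no rate. The main consequence is for diagnosis and coding; overall AE or SAE percentages are unlikely to change much. The unblinding route through the medical record is possible but conditional on the saline container and on what is written down. This is an inconsistency to correct in wording and does not put the study's conclusions in doubt.

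**What to change.** Amend 10.6.4 so that:

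1. Unblinded staff describe the deficiency on the Medical Device Complaint form and refer any possible injury to the blinded investigator.
2. The blinded investigator makes the diagnosis and records the AE or SAE under 10.3.3, consistent with 8.3.9.
3. Details that could reveal the assignment, such as container type and arm, are held in the unblinded file instead of the shared medical record, except where the investigator needs them for the device-causality assessment.
4. Existing timelines continue to apply: the 24-hour reporting of SAE-associated deficiencies in 10.6.6, and the causality assessment that 10.6.4 requires before an SAE is first transmitted.

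The IP manual should be checked for matching wording. The cost is a text change with no new visits or data. The small downside is that the investigator assesses device causality with limited device detail unless more is needed.
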